9.4.3 ANALYSIS OF THE SECONDARY ENDPOINT

Preliminary analyses of the survey data (sexual violence victimization and perpetration, rape myth acceptance, and sexual relationship power) will be analyzed using the Statistical Package for the Social Sciences (SPSS); all p-values will be set at $<.05$. Descriptive statistics will be assessed first. The baseline, 3-month post, and 6-month post-intervention tests will be examined for measures of central tendency, measures of dispersion, and frequency distribution on outcomes. Analysis of variance (ANOVA) will be utilized to determine if the scores on the baseline and follow-up tests differ significantly among the two arms. Usability and acceptability scores will be assessed among those in the intervention group.

We are not powered to assess outcome measures (sexual violence experiences/behaviors, rape myth acceptance, relationship power); however, we will look at the direction of effects for our outcome measures to allow for power calculations for future scale-up.

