4 STUDY DESIGN

4.1 OVERALL DESIGN

This project builds on the current momentum to address the primary prevention of sexual violence within United States institutions of higher education as well as the proliferation of web-based applications. We will test a culturally and contextually adapted evidence-based application, MKit, with incoming university students (age range expected to be 18-25 years old) using the ADAPT-ITT (Assessment, Decision, Adaptation, Production, Topical experts, Integration, Training, Testing) framework (Wingwood & DiClemente, 2008). The web-based application was created through collaboration with students, stakeholders, and topical experts and developed by the Center for Health Communications Research (CHCR) through a modification of the pre-existing iCON platform. This process will allow us to translate clinical research on the life skills approach to impact the health and well-being of university students.

A before-and-after quasi-experimental, mixed-method pilot design will be used to gather acceptability and safety data as well efficacy trends. Two residence halls (West Quad and South

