Quad) at the University of Michigan will be randomized to receive either: (1) the control arm (n=150) which will receive usual care only (all incoming students receive three programs about healthy relationships and sexual violence including Haven, Relationship Remix, and Change it Up) or (2) the usual care (n=150) described above and the web-based intervention (MKit). We will use cluster-randomization by residence hall (to minimize contamination associated with individual-level randomization of students living in the same residence hall). Following the informed consent process, students in both conditions will complete a baseline survey of 85 questions. Baseline measures will include: 1) demographic data, 2) 20 items from the Sexual Experiences Survey (SES) will measure past experiences with sexual violence (Koss et al., 2007), 3) investigator developed questions on knowledge about sexual violence, 4) 22 items from the modified Illinois Rape Myth Acceptance Scale to measure attitudes endorsing rape myths (McMahon & Farmer, 2011), and 4) 6 items from the Sexual and Relationship Power Scale (SRPS) will measure the multidimensional nature of power in relationships (Pulerwitz & Barker, 2000). All of these are measures have been validated and used extensively in the United States to measure knowledge and attitudes related to gender based violence. Following the survey, students in the Intervention group will be given the opportunity to interact with the application at their own pace, choosing which content to view in the order they prefer.

The Control group will only receive the usual care delivered to all incoming University of Michigan students, which includes Haven (an online course about sexual violence), Relationship Remix (an interactive program about healthy relationships and sexual violence delivered by peers), and Change it Up (a theater based performance on bystander intervention). The Intervention group will receive the usual care described above as well as access to the adapted web-based application. They will be encouraged to interact with the web-based application throughout the study. Data will be collected on the content viewed by the participants, as well as the amount of time they spend within each content area, and the order in which they view the content.

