4.4 END OF STUDY DEFINITION

A participant is said to have completed the study if he or she has completed all three surveys, including the baseline, 3-month, and 6-month surveys, shown in the SOA.

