5.5 STRATEGIES FOR RECRUITMENT AND RETENTION

Students from the target sample, first-year University of Michigan college students, will be recruited for the study. Two residence halls (West Quad and South Quad) at the University of Michigan will be randomized to receive either: (1) the control arm (n=150) which will receive usual care only (all incoming students receive three programs about healthy relationships and sexual violence including Haven, Relationship Remix, and Change it Up) or (2) the usual care (n=150) described above and the web-based intervention (MKit). We will use cluster-randomization by residence hall (to minimize contamination associated with individual-level randomization of students living in the same residence hall). At the end of the Relationship Remix program, a brief announcement will be made about the opportunity to participate in a research study about healthy relationships and palm cards will be distributed (see recruitment materials). We will recruit specifically from Relationship Remix to ensure that all experimental and control subjects receive the same primary prevention programming currently in place on campus. Interested students will receive a palm card with a link to either the MKit web-based application (Intervention) with an access code to sign-up for the website, or a link to the baseline consent and Qualtrics survey (Control) without access to the web-based application. At the end of the study, students from each condition will be invited to participate in an in-person semi-structured interview. Students will receive the invitation to participate in the semi-structured interview on the final page of their 6-month follow-up survey. Students who opt to share their email address with the study team at that time will be contacted to set-up an in-person interview based on user status for the intervention (consistent user of MKit, frequent user of MKit, minimal user of MKit) and a diverse group based on gender, race/ethnicity, and age for the control group. Semi-structured interviews will be conducted with participants from both the Control group (n=10) and the Intervention group (n=15).

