9.3 POPULATIONS FOR ANALYSES

All data collected through the pilot study process will be utilized for the analyses related to feasibility, usability, and acceptability. The data collected from the semi-structured interview subjects will be utilized to analyze the safety of the application and the willingness of participants to use the application.

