9.4.8 TABULATION OF INDIVIDUAL PARTICIPANT DATA

Individual participant data will be listed by measure and time point.

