10.1.3 CONFIDENTIALITY AND PRIVACY

Participant confidentiality and privacy is strictly held in trust by the participating investigators, their staff, and the sponsors and their interventions. Therefore, the study protocol, documentation, data, and all other information generated will be held in strict confidence. No information concerning the study or the data will be released to any unauthorized third party without prior written approval of the sponsor.

All research activities will be conducted in as private a setting as possible. Study participants can choose to interact with the WebApp and take study surveys whenever is comfortable and safe for them to do so.

The information we collect will only be seen by the research team. We will not link the email address or any identifiable information of any participant to any of the survey or application use data collected. All data will be reported in aggregate. Research data will be stored on a secure,

HIPAA-compliant server and drive with monitored and controlled access for study staff and investigators. The web-based survey will be hosted on secure servers.

The WebApp is hosted on virtualized servers provided by the University of Michigan Information Technology Services group. The virtualized servers are housed at two redundant data centers. These data centers provide protection from lengthy outages, 24/7 staffing, restricted physical access and disaster recovery. Virtual servers are backed up automatically onto encrypted tape for recovery and security. The data centers also reduce the use of physical resources such as electricity and air conditioning.

All servers and the back end databases are password protected. The server runs the RedHat Linux 7 Enterprise operating system. Security patches and updates are downloaded and installed automatically. Each server is also protected by firewalls to restrict network access to the server. The study web application software communicates directly with the database on the same server so unencrypted participant data is not transmitted on the Internet.

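### The between-arm ANOVA for the exploratory efficacy scores names no tested effect and makes no use of the baseline score, so a standing difference between the two halls can pass for an app effect (minor)

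*Combined protocol and SAP*

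**What the plan says.** Section 9.4.3 states the method for rape myth acceptance, relationship power and sexual violence experiences: "Analysis of variance (ANOVA) will be utilized to determine if the scores on the baseline and follow-up tests differ significantly among the two arms". Section 9.4.1 repeats the sentence word for word. Neither names a factor, contrast, wave or covariate. Section 9.4.5 compares the arms on personal characteristics only, not on outcome scores.

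On design, Section 4.1 says: "A before-and-after quasi-experimental, mixed-method pilot design will be used to gather acceptability and safety data as well efficacy trends". On allocation, Section 5.5 says: "Two residence halls (West Quad and South Quad) at the University of Michigan will be randomized to receive either" usual care alone or usual care plus the app. That is one hall per arm, with 150 students in each.

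The data rule in Section 9.3 is: "All data collected through the pilot study process will be utilized for the analyses related to feasibility, usability, and acceptability". Its next sentence covers safety and willingness. The efficacy scores are not mentioned.

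Sections 9.4.3 and 9.4.9 state that the study is not powered for these outcomes and that the direction of effects will serve future power calculations.

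**The concern.** With one hall per arm, arm and hall are the same variable, and randomizing two halls cannot be expected to balance their residents. What happens to a prior difference between the halls therefore depends on which effect the ANOVA tests. Three readings fit the sentence:

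- a separate test at each wave, which is the most literal;
- an arm main effect over all three waves, which is less natural for a before-and-after design;
- an arm-by-time effect, which the design label hints at but Section 9 never states.

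The first two pass a constant hall difference through in full. Only the third compares change. At stake are the direction and size of effect that the pilot is meant to hand on to the next study.

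**Working it through.** The plan has no power figure, SD or effect size to reproduce; Section 9.2 says that no formal calculation was done.

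**Inputs from the documents:** 150 per arm; alpha 0.05; one hall per arm; waves at baseline, 3 and 6 months.

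**Assumptions, not in the documents:** two-sided test; SD 1; constant hall gap g = 0.1, 0.2 or 0.3 SD; equal correlation between waves r = 0.3 / 0.5 / 0.7; no app effect unless stated; within-hall clustering ignored, as a plain ANOVA would.

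**1. What each contrast estimates with no app effect.** Per-wave test: g. Arm main effect: g. Baseline-adjusted (ANCOVA) difference: g(1 − r). Change from baseline: 0. These follow from algebra and do not depend on the size of g.

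**2. Rejection by a follow-up-only test.** SE = sqrt(2/150) = 0.1155.
- g = 0.1: z = 0.87, rejection 14%
- g = 0.2: z = 1.73, rejection 41%
- g = 0.3: z = 2.60, rejection 74%

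The change contrast has expectation 0, so it rejects in 5%.

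**3. The other contrasts at g = 0.2.** Arm main effect: z = 0.2 / sqrt(((1 + 2r)/3) × 2/150) = 2.37 / 2.12 / 1.94, rejection 66 / 56 / 49%. ANCOVA: z = 0.2(1 − r) / sqrt((1 − r²) × 2/150) = 1.27 / 1.00 / 0.73, rejection 25 / 17 / 11%.

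**4. A reader who also looks at the baseline test.** Treat the baseline and follow-up z values as bivariate normal, each with mean g/0.1155 and correlation r. The misleading pattern is follow-up significant and baseline not:

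| Gap | r = 0.3 | r = 0.5 | r = 0.7 |
|---|---|---|---|
| none | 4.5% | 4.1% | 3.3% |
| 0.1 SD | 10% | 9% | 7% |
| 0.2 SD | 20% | 16% | 12% |

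**5. Direction of effect.** Take a gap of +0.3 SD and a true app effect of −0.3 SD at both follow-ups. The per-wave estimate is 0.3 − 0.3 = 0. The main effect is (0.3 + 0 + 0)/3 = +0.10, the wrong sign. Change gives 0 − 0.3 = −0.30.

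**6. What the change contrast does not remove.** Suppose one hall drifts by 0.2 SD after baseline and the app does nothing. Then z = 0.2 / sqrt(2(1 − r) × 2/150) = 1.46 / 1.73 / 2.24, rejection 31 / 41 / 61%.

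**7. Price in precision.** The variance of change relative to ANCOVA is 2(1 − r)/(1 − r²) = 1.54 / 1.33 / 1.18. The 95% CI half-widths are 0.27 / 0.23 / 0.18 SD for change and 0.22 / 0.20 / 0.16 SD for ANCOVA.

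**The case against.** The strongest reply is that little hangs on this. The outcomes are secondary, preliminary and declared unpowered, and no decision depends on p<.05. That stands and sets the severity. It does not remove the point, because direction and size are the stated use of these data.

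A second reply is that the same sentence also tests baseline, so a careful reader would see a gap. This is partly right, and step 4 is the fairer measure for such a reader. The misleading pattern is still more frequent than with no gap, and the plan does not say how a baseline difference would be used.

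Third, the root problem is one hall per arm, which no choice of contrast cures. That stands; step 6 puts a size on it.

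Three stronger readings should be resisted:

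- A reader might take the 49 to 66% for the arm main effect as the headline. That reading is possible but is the less natural one for a before-and-after design.
- A reader might infer that the repeated Sexual Experiences Survey (SES) dilutes new events with old ones. Section 4.1 says of baseline that "20 items from the Sexual Experiences Survey (SES) will measure past experiences with sexual violence", and the measures are repeated at follow-up with no stated recall window. The item wording and its reference period are not in the documents, so this is a query and not a finding.
- A reader might infer from Section 10.1.3, "We will not link the email address or any identifiable information of any participant to any of the survey or application use data collected", that one student's surveys cannot be joined. That bars linking identifiers, not a de-identified code. Section 4.4 ("A participant is said to have completed the study if he or she has completed all three surveys") and Section 9.4.8 ("Individual participant data will be listed by measure and time point") imply linkage, although no code is described.

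**Conclusion.** The point holds as a minor one. The tested effect is not named and the baseline score is not used. With one hall per arm, the literal per-wave reading passes a constant hall difference in full into the apparent app effect. That conclusion needs no assumed numbers. The rejection rates do: they rest on the assumed gaps, on equal correlation between waves and on ignoring clustering.

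The 5% for the change contrast should not be read as protection against confounding by hall. It holds only if the halls differ by a constant. The usability, acceptability, safety and willingness endpoints are unaffected.

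**What to change.** In Sections 9.4.1 and 9.4.3, for rape myth acceptance and relationship power:

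- Replace the bare ANOVA with a linear mixed model, available in SPSS, with arm, time and arm-by-time. Use all available baseline, 3- and 6-month scores, including students with baseline only, and state this as the efficacy analysis set.
- Report the difference between arms in change from baseline at each follow-up with a 95% CI, and show the baseline-adjusted (ANCOVA) difference beside it.
- Report the SD and the baseline-to-follow-up correlation, which the next power calculation needs.
- Label the results descriptive, because with one hall per arm no model separates app from hall.
- Confirm that a de-identified code joins each student's surveys, and describe it.

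For the SES, as a query only: check the questionnaire's reference period at each wave. If it is open-ended, follow-up totals mix prior with new events and should be described so.

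Cost: plan wording and a little more analysis, with no extra participants, visits or measures. The change contrast is less precise than ANCOVA (step 7), which is why both should be shown. If no linking code exists, the cost is more than wording. Changing SES item wording would be an amendment needing IRB approval.

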9.4.4 SAFETY ANALYSES

The safety of the WebApp will be assessed through post-intervention semi-structured interviews, conducted with 25 participants including 15 participants from the intervention group and 10 participants from the control group.

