1.2 SCHEMA

1.3 SCHEDULE OF ACTIVITIES (SOA)

Procedures	Preparation before recruitment	Baseline	3-month follow-up	6-month follow-up	Post-study semi-structured interviews
Randomization by residence hall	X				
Demographics		X	X	X	
Healthy Relationship Knowledge Questions		X	X	X	
Illinois Rape Myth Acceptance Scale – Modified		X	X	X	
Sexual Experiences Survey		X	X	X	
Sexual Relationship Power Scale		X	X	X	
System Usability Scale			X	X	
System Acceptability			X	X	
User Data			X	X	
Reaction to content					X
Perceived safety					X
Desirability					X
Willingness for future use					X

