3 OBJECTIVES AND ENDPOINTS

Objectives	Endpoints	Justification for Endpoints
Primary		
To evaluate the safety, usability, acceptability, and willingness of using the adapted WebApp among a randomized sample of 300 first year university students.	Safety will be assessed through qualitative interviews Usability will be measured through the System Usability Scale (Brooke, 1986)	The endpoints are common outcomes of interest for studies of technological interventions. These outcomes will be measured throughout the study, to observe changes overtime with continued exposure to

	
Acceptability will be measured through an investigator generated scale
 
Willingness to use will be assessed through qualitative interviews
	
the intervention. These endpoints are important outcomes, as interventions must be safe, acceptable, and usable to ensure broad scale uptake.
	
Secondary	
To complete preliminary evaluations on efficacy measures such as sexual victimization/perpetration, rape myth acceptance, and power in sexual relationships to allow for power calculations for a future R-level submission.
	
Sexual victimization/perpetration will be measured using the Sexual Experiences Survey (Koss et al., 2007)
 
Rape myth acceptance will be measured using the Illinois Rape Myth Acceptance – Modified (McMahon & Farmer, 2011)
 
Relationship power differentials will be measured using the Sexual Relationship Power Scale (Pulerwitz, Gortmaker, & DeJong, 2007)
	
The endpoints are important, as the WebApp under study is a primary sexual violence prevention intervention. As such, experiences of sexual violence victimization and perpetration, as well as rape myth acceptance and relationship power (both upstream factors contributing to sexual violence perpetration) are outcomes of interest. Though this pilot study is not powered to detect changes in these secondary outcomes, obtaining data for power calculations for a larger study is a key component of this study.

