4.2 SCIENTIFIC RATIONALE FOR STUDY DESIGN

This is a before-and-after quasi-experimental, mixed-method pilot design with three survey collection points and a post-study semi-structured interview component. This study will be performed with healthy college students to determine the safety, acceptability, and usability of the WebApp.

The endpoints are common outcomes of interest for studies of technological interventions. These outcomes will be measured throughout the study, to observe changes over time with continued exposure to the intervention. These endpoints are important outcomes, as interventions must be safe, acceptable, and usable to ensure broad scale uptake. As the WebApp under study is a

primary sexual violence prevention intervention, experiences of sexual violence victimization and perpetration, as well as rape myth acceptance and relationship power (both upstream factors contributing to sexual violence perpetration) are outcomes of interest. Though this pilot study is not powered to detect changes in these secondary outcomes, obtaining data for power calculations for a larger study is a key component of this study.

This study compares usual care for the prevention of sexual violence with care as usual plus the intervention. Both groups will receive interventions currently in place, ensuring that standard care is not withheld from any participant. As the intervention under study is intended to supplement and reinforce current primary prevention programming, the study design will measure the acceptability and preliminary efficacy of broad scale-up of the intervention to the broader college campus.

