9.4 STATISTICAL ANALYSES

9.4.1 GENERAL APPROACH

The survey data will be analyzed using the Statistical Package for the Social Sciences (SPSS); all p-values will be set at $<.05$. Descriptive statistics will be assessed first. The baseline, 3-month post, and 6-month post-intervention tests will be examined for measures of central tendency, measures of dispersion, and frequency distribution on outcomes. Analysis of variance (ANOVA) will be utilized to determine if the scores on the baseline and follow-up tests differ significantly among the two arms. Usability and acceptability scores will be assessed among those in the intervention group.

We are not powered to assess outcome measures (sexual violence experiences/behaviors, rape myth acceptance, or sexual relationship power); however, we will look at the direction of effects for our outcome measures to allow for power calculations for a future R-Level submission. The results of this project will establish the safety and usability of this adapted web-based application for future scale-up.

For the semi-structured interviews, all audiotapes will be transcribed verbatim. Data analyses will be conducted using an iterative process and the constant comparative method of analysis (Glaser, 1992). Member checking will contribute to credibility through validation of the research findings by participants. A codebook will be developed after repeated high-level reading of the transcripts by the study team. Data will be coded and grouped into categories to facilitate abstraction and concept analysis.

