9.4.2 ANALYSIS OF THE PRIMARY ENDPOINT

The safety of the WebApp and the willingness of participants to use the WebApp will be assessed through post-intervention semi-structured interviews, conducted with 25 participants including 15 participants from the intervention group and 10 participants from the control group. The usability for the WebApp will be assessed at two time points (3-months and 6-months) using the 10-item System Usability Scale (Brooke, 1996). The acceptability of the WebApp will be assessed at two time points (3-months and 6-months) using an investigator created 5-item acceptability scale. Usability and acceptability scores will be assessed among those in the intervention group.

For the semi-structured interviews, all audiotapes will be transcribed verbatim. Data analyses will be conducted using an iterative process and the constant comparative method of analysis (Glaser, 1992). Member checking will contribute to credibility through validation of the research findings by participants. A codebook will be developed after repeated high-level reading of the transcripts by the study team. Data will be coded and grouped into categories to facilitate abstraction and concept analysis. An audit trail will be established to allow others to follow the decisions made by the research team (Sandelowski & Barroso, 2003). The results of the semi-structured interviews will be used to: 1) update the content of the WebApp, as needed; 2) assess the safety of the WebApp; 3) assess the usability and willingness to use the WebApp; and 4) assess the acceptability of the WebApp.

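### The primary safety endpoint rests on 25 opt-in interviews after the 6-month survey, 15 of them with students offered the app, and recorded adverse events enter no analysis; this can describe perceived safety but not establish safety

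*Combined protocol and SAP*

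**What the plan says.** Section 3 lists safety, usability, acceptability and willingness to use as primary endpoints and assigns safety and willingness to qualitative interviews. Section 9.3 makes the interviewees the analysis population for both: "The data collected from the semi-structured interview subjects will be utilized to analyze the safety of the application and the willingness of participants". Section 9.4.2 repeats this: "The safety of the WebApp and the willingness of participants to use the WebApp will be assessed through post-intervention semi-structured interviews". Section 9.4.4 on safety reads "The safety of the WebApp will be assessed through post-intervention semi-structured interviews, conducted with 25 participants including 15 participants from the intervention group", with the remaining 10 from the control group, and names no other source.

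Under Section 5.5, the interview invitation appears on the final page of the 6-month survey, and students who choose to give an email address may be contacted. Intervention interviewees are to be chosen by level of app use. Controls receive no access to the app.

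Section 8.3.4 requires all adverse events (AEs) on study to be documented, and Sections 8.3.5 and 8.3.6 require them to be reported to the sponsor. Section 10.1.8 provides an email route for problems with the app and surveys.

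Two broader statements matter. Section 9.4.1: "The results of this project will establish the safety and usability of this adapted web-based application for future scale-up". Section 4.2, of the primary outcomes: "These outcomes will be measured throughout the study, to observe changes over time with continued exposure to the intervention"; Section 3 says the same. In the schedule (Section 1.3), the rows for perceived safety and "Willingness for future use" are marked only at the post-study interview.

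**The concern.** The planned conclusion is stronger than the data behind it. A small, self-selected group interviewed once, at the end, can show what problems students describe. It cannot show that harms are absent or rare, and it includes nobody who left before finishing the 6-month survey. A student upset by the content who then withdrew is one the safety assessment should hear from and will not.

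The study must also document AEs for everyone enrolled, yet Section 9.4.4 does not use those records. A reader of the final report could therefore meet a statement that safety has been established, offered in support of scale-up, with the study's own event records left out of the analysis.

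**Working it through.** **1. Planned figures.** Section 9.2 states that no sample size calculation was done, so there is no precision figure to reproduce. The counts agree: 15 + 10 = 25 interviews and 150 + 150 = 300 students. The app-offered interviewees are 15/150 = 10% of their arm.

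**2. Who can inform app safety.** The 10 control interviewees had no access, and no section says how their interviews bear on app safety. That leaves 15. Exposure among them varies, because "students in the Intervention group will be given the opportunity to interact with the application at their own pace". Use is recorded (Sections 1.3 and 4.1), and consistent, frequent and minimal users are the planned groups (Section 5.5).

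**3. What 15 interviews could exclude.** This is an illustration only. The documents give no harm rate, the sample is opt-in and purposive, and the binomial model assumes random sampling.

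- Zero-event upper bound, one-sided 95%: 1 − 0.05^(1/n). For n = 15: 1 − 0.05^(1/15) = 18.1%. Two-sided: 1 − 0.025^(1/15) = 21.8%.
- Chance that all 15 are free of a harm with true rate p: (1 − p)^15.

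| Assumed p | Chance of missing it |
|---|---|
| 1% | 0.99^15 = 86% |
| 5% | 0.95^15 = 46% |
| 10% | 0.90^15 = 21% |

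- Number needed, with zero events, to exclude a 5% rate: ln(0.05)/ln(0.95), rounded up, = 59.

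**4. Effect of selection.** Suppose harmed students take part r times as often as others (r is assumed; the documents give no value). The rate among participants is q = pr/(pr + 1 − p). For p = 5% and r = 0.5, q = 0.025/0.975 = 2.56%, and the chance of missing the harm in 15 interviews rises to (1 − 0.0256)^15 = 68%.

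**5. What a survey item could add.** With zero events, the one-sided bound would be 3.9% with 75 responders and 2.0% with all 150 (assumed response numbers). With r = 0.5, 75 responders would miss a 5% harm with probability (1 − 0.0256)^75 = 14.3%. These figures assume that a fixed item detects harm as well as an interview does, which favours the survey.

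**6. AE capture.** Section 8.3.4 expects events to come to notice at study visits and interviews. The schedule has surveys followed by interviews, with no other visits. Capture is therefore passive, and a low count would say little.

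**7. Timing.** Usability and acceptability are marked at 3 and 6 months, so the statement in Sections 3 and 4.2 that outcomes are measured throughout holds for them. For safety and willingness the schedule has one time point, so no change over time can be observed.

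**The case against.** This is a minimal-risk pilot with numbers set by feasibility, and qualitative interviews are a proper way to learn about perceived safety, the label used in Sections 1.3 and 4.1. The next step is a powered study, and the interviews also serve to improve the app's content. On this view the harm is one over-strong sentence, and binomial bounds on a purposive sample prove little. Much of this stands: the interviews should stay, and the figures only illustrate scale. It does not rescue the sentence in Section 9.4.1 or explain why recorded AEs are left out.

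A reader might infer more than the documents support:

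- **That a clean set of interviews triggers a declaration of safety.** The plan contains no such rule; Section 9.4.1 speaks of the project's results as a whole.
- **That app exposure is unknown.** Use is recorded and guides selection of interviewees. Whether it can be linked to individual interviewees is unclear, given the no-linkage rule in Section 10.1.3.
- **That students who stopped using the app are excluded.** They are not, provided they reach the end of the 6-month survey.
- **That willingness is overclaimed in the same way.** Section 9.4.1 mentions only safety and usability.
- **That participants are unprotected.** AE reporting (Sections 8.3.5 and 8.3.6) and provisions for suspension (Section 10.1.2) exist and are not in dispute here.

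**Conclusion.** The point holds for the safety conclusion. The plan supports a qualitative description of perceived safety among students who completed the 6-month survey and volunteered. It does not support the statement that safety will be established, and it leaves recorded AEs out of the safety analysis. The 18.1% bound and 46% miss probability rest on random sampling and, for the latter, an assumed 5% rate; the opt-in route gives no assurance of the first.

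For willingness, the only defect is that the timing stated in Sections 3 and 4.2 conflicts with the schedule. The study can run as designed, but the analysis section and the wording should be corrected.

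**What to change.** 1. **Section 9.4.4:** report recorded AEs and serious AEs by arm beside the interview findings. List app problem reports (Section 10.1.8) for the intervention arm only, since controls have no app. State that capture was passive, so low counts are not evidence of no harm.
2. **Interviews:** base conclusions about app safety on the intervention interviewees, describe their exposure from recorded use where linkage permits, and report the control interviews separately.
3. **Wording:** in Section 9.4.1, say that the results will describe perceived safety. In Sections 3 and 4.2, limit the statement about measurement throughout the study to usability and acceptability.

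These need a listing of data the study already collects and an IRB-approved amendment. The price is a less absolute safety claim.

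**Optional:** add one or two fixed items on distress from content, or a privacy or safety problem, to the intervention arm's 3- and 6-month surveys. Report proportions with exact 95% confidence intervals and the number of non-responders. The cost is slightly longer surveys in one arm. Non-response remains, and a fixed item may detect less than an interview. Survey data are not linked to identity (Section 10.1.3), while Sections 8.3.4 and 8.3.5 require AEs to be followed and reported, so the plan must reconcile these before adding such items.
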